3.4 Efficacy Analyses

The efficacy analysis will be based on the As-treated Population. Sensitivity analyses for response-related endpoints (OR, DoR, and DCR) will be performed based on the Response Evaluable Population.

Primary analyses for response-related endpoints and corresponding time-to-event endpoints for primary and secondary efficacy endpoints will be based on the programmatically-derived response from the investigator's recorded measurements and assessments for target, non-target, and new lesions according to RECIST v1.1 or blinded independent central review (BICR) if performed.

3.4.1 Primary Efficacy Endpoints and Analyses

Arms A, B, C and E

The two co-primary efficacy endpoints are Objective response (OR) and PFS-6 based on RECIST v1.1.

Arm D

The primary efficacy endpoint is objective response (OR) based on RECIST v1.1.

The primary efficacy analyses for the primary efficacy endpoint(s) will be based on the As-treated Population.

Objective Response

Objective response (OR) is defined as best overall response (BOR) of confirmed CR or confirmed PR according to RECIST v1.1. The best overall response is defined as the best response (in the order of CR, PR, SD, PD, and not evaluable) among all overall responses recorded from the date of randomization for Phase 2 Arm A, B and C subjects or the date of first dose of study treatment for Phase 1b and Phase 2 Arm D and E subjects until progression, or the last evaluable disease assessment in the absence of PD prior to the initiation of subsequent anticancer therapy or discontinuation from the study, whichever occurs first.

The best overall response (BOR) of CR or PR must be confirmed, which means a response of CR/PR is recorded at 1 visit and confirmed by repeat imaging not less than 28 days (4 weeks) after the visit when the response was first observed with no evidence of progression between the initial and CR/PR confirmation visit. A confirmed CR is defined as two CRs that were

separated by at least 28 days with no evidence of progression in-between. A confirmed PR is defined as two PRs or an un-confirmed PR and an un-confirmed CR that were separated by at least 28 days with no evidence of progression in-between. For a subject to qualify for a BOR of SD, at least 54 days from the randomization date or start of treatment date must elapse without disease progression. The definition of 54 days reflects the protocol-defined disease assessment window of ± 3 days (Day 57 plus/minus 3 days).

Subjects who responded with an unconfirmed CR/PR at the time of data cutoff will be reported as CR/PR pending confirmation under the SD category provided the minimum criteria for SD duration (54 days) are met, otherwise this will be reported under the Non Evaluable (NE) category. NE is assigned for a subject who has only a baseline assessment, or a response assessment of CR/PR/SD at an interval of less than 54 days since randomization or the start of treatment and who has no subsequent disease evaluation, or has all overall response evaluations assessed as NE.

The ORR is defined as the proportion of subjects with OR. The 2-sided 90% and 95% CI of ORR will be estimated based on the exact probability method. In addition, to help make a comparison to historical data, the unconfirmed ORR which is defined as the proportion of subjects who achieved a best overall response of confirmed/unconfirmed CR or confirmed/unconfirmed PR will be presented along with its CI.

ORR will be compared between the three treatment groups (Arm A, B and C). P-values will be presented without multiplicity adjustment. The comparisons will include the following:

- MEDI4736 + tremelimumab combination therapy (Arm A) versus MEDI4736 monotherapy (Arm B)
- MEDI4736 + tremelimumab combination therapy (Arm A) versus tremelimumab monotherapy (Arm C)

P-values for comparisons of ORR between the treatment groups mentioned above will be obtained from Fisher's exact test. The statistical significant treatment difference will be tested against 2-sided alpha level of 0.05. In addition, the difference in ORR between MEDI4736 + tremelimumab combination and MEDI4736 monotherapy or tremelimumab and associated 95% exact unconditional confidence interval will be provided using Agresti and Ming (2001)'s approach by specifying the RISKDIFF(METHOD=FMSCORE) option in PROC FREQ.

PFS-6

PFS-6 is 6-month progression-free survival rates, which is the proportion of subjects who are progression free and alive at 6 months. PFS is defined as the time from the date of randomization for Phase 2 Arm A, B and C subjects or the date of first dose of study treatment for Phase 1b and Phase 2 Arm D and E subjects to the earlier of the dates of the first objective documentation of radiographic disease progression (per RECIST v1.1) or death due to any cause.

For subjects who are alive with no objective documentation of (radiographic) disease progression by the data cutoff date, PFS will be censored at the date of their last evaluable tumor assessment. If the subject progresses or dies after ≥ 2 consecutively missed or non-evaluable disease assessment visits, PFS will be censored at the time of the latest evaluable disease assessment prior to the missed assessments.

In this study, progression or death after ≥ 2 consecutive missed disease assessment visits is defined (according to disease assessment schedules specified in the protocol) as below:

- ≥ 18 weeks (two disease assessment visits plus 2 week visit window to allow for a late assessment) since the last post-baseline evaluable disease assessment, if progression or death occurs prior to end of treatment.
- ≥ 26 weeks (three disease assessment visits plus 2 week visit window to allow for a late assessment) since the last post-baseline evaluable disease assessment, if progression or death occurs after end of treatment.

The details of censoring rules are listed in table 3.4.1-1.

Table 3.4.1-1 Summary of Censoring Guidelines for PFS

Situation	Date of PD/Death or Censoring	PFS Outcome
Documented Progressive Disease (PD)	Date of earliest sign of PD	Event
Death prior to second scheduled post-baseline disease assessment or after ≤1 missed or non-evaluable disease assessment following an adequate post-baseline disease assessments	Date of death	Event
No PD or death at time of analysis or lost to follow-up	Date of last adequate progression-free disease assessment	Censored
Death or PD immediately after ≥ 2 consecutive missed or non-evaluable disease assessments	Date of randomization/the first dose of study treatment or last progression-free disease assessment prior to missed or non-evaluable assessments, whichever occurred last	Censored
Initiation of alternative anticancer therapy before PD or death	Date of last adequate progression-free disease assessment prior to initiation of alternative anticancer therapy	Censored
No tumor assessment at baseline and no death prior to second scheduled post-baseline disease assessment, or no tumor assessment post-first dose	Date of randomization/the first dose of study treatment	Censored

Kaplan-Meier curves will be generated for PFS and used to estimate the PFS-6 along with its 2-sided 90% and 95% CIs. The CIs for PFS-6 will be calculated by applying asymptotic normality to the log-log transformation of PFS-6.

PFS-6 will be compared between the three treatment groups (Arm A, B and C). P-values will be presented without multiplicity adjustment. The comparisons will include the following:

- MEDI4736 + tremelimumab combination therapy (Arm A) versus MEDI4736 monotherapy (Arm B)
- MEDI4736 + tremelimumab combination therapy (Arm A) versus tremelimumab monotherapy (Arm C)

The comparison of PFS-6 will be performed by normal approximation under log-log transformation of Kaplan-Meier estimates of PFS-6 ([Klein et al, 2007](#)).

Specifically, the log HR (1 for combination vs 2 for monotherapy) is estimated as

$$\log(-\log(\hat{S}_1(t))) - \log(-\log(\hat{S}_2(t)))$$

The variance for log HR is estimated as

$$\frac{Var(\hat{\zeta}_1(t))}{\hat{\zeta}_1(t)(\log(\hat{\zeta}_1(t)))^2} + \frac{Var(\hat{\zeta}_2(t))}{\hat{\zeta}_2(t)(\log(\hat{\zeta}_2(t)))^2}$$

where $\hat{\zeta}(t)$ is the Kaplan-Meier estimate of the progression free survival function, $Var(\hat{\zeta}_i(t)) = \hat{\zeta}_i(t)^2 \sum_{t_{ik} \leq t} \frac{d_{ik}}{n_{ik}(n_{ik}-d_{ik})}$ is the variance for $\hat{S}_i(t)$ derived from Greenwood's formula. d_{ik} and n_{ik} refer to the number of events and number of subjects at risk in the i^{th} group at time t_{ik} , respectively. The final estimate of HR and corresponding 95% CI will be obtained by taking the exponential of log HR and its 95% confidence limits.

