2.4.1 Phase 1b

A safety run-in of up to 9 subjects will be required to investigate the safety and tolerability of the dose level and schedule selected for dose expansion in Study D4190C00006. The sample size for Phase 1b of the study is not based on formal statistical power considerations.

2.4.2 Phase 2

Arms A, B and C (Prior to Protocol Amendment 6)

Approximately 125 subjects will be randomly assigned in a 2:2:1 ratio to Arms A, B, or C. Assuming 10% of the subjects are not evaluable for response or drop-out without a progression free survival (PFS) event before 6 months participation, approximately 45 evaluable subjects for either Arm A or B, and approximately 22 evaluable subjects for Arm C are expected. The sample size determination is based primarily on the consideration of providing the estimation with reasonable precision. As shown in [Table 2.4.2-1](#), when the ORR is expected to be in the 29% to 40% range, a total of 45 subjects would provide a width of 11% to 12% between the observed point estimator and its lower limit of the exact 90% CI. If 24 of 45 subjects have PFS \geq 6 months, the PFS-6 will have an estimate of 53% with a 90% CI of (41%, 65%). Assuming that PFS follows an exponential distribution, the PFS-6 of 53% will correspond to a median PFS of 6.6 months, which is a 50% increase from the 4.4 months observed for ramucirumab plus paclitaxel in subjects with metastatic gastric or GEJ adenocarcinoma following disease progression on first-line platinum- and fluoropyrimidine-based combination therapy in the RAINBOW study ([Wilke et al, 2014](#))

Table 2.4.2-1 Observed ORR and PFS-6 with 90 Percent CI (Arms A and B)

N	Number of Subjects with OR	ORR	2-sided Exact 90% CI	
45	13	29.0%	18%	42%
45	18	40.0%	28%	53%

N	Number of Subjects with PFS at 6 Months	PFS-6	2-sided 90% CI	
45	24	53.0%	41%	65%

OR = objective response; ORR = objective response rate; PFS-6 = progression free survival 6 months

With 45 evaluable subjects for either Arms A or B in Phase 2, the study will have > 90% probability to select the superior regimen if the true difference between the response (or PFS-6) rates in those 2 treatment arms is \geq 14%. In addition, assuming the prevalence of

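### SAP 3.4.1 tests ORR with Fisher's exact test but reports an exact unconditional score interval, so the interval can exclude zero while the test is not significant; the power cost is real for Arm A vs B and small for Arm A vs C

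*SAP*

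**What the plan says.** SAP 3.4.1 (Objective Response) compares ORR for Arm A vs Arm B and Arm A vs Arm C.

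- Test: "P-values for comparisons of ORR between the treatment groups mentioned above will be obtained from" Fisher's exact test.
- Level: "The statistical significant treatment difference will be tested against 2-sided alpha level of 0.05".
- Multiplicity: "P-values will be presented without multiplicity adjustment".
- Interval for the difference: "associated 95% exact unconditional confidence interval will be provided using" a cited approach, "by specifying the RISKDIFF(METHOD=FMSCORE) option in PROC FREQ". This is a Farrington-Manning score interval.

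The visible text does not say whether the p-value or the interval governs interpretation. It also does not say whether the interval inverts one two-sided test or two one-sided tests.

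On size, SAP 2.4.2 plans about 125 subjects at 2:2:1 and, after 10% loss, "approximately 45 evaluable subjects for either Arm A or B, and approximately 22 evaluable subjects for Arm C are expected". The efficacy analysis uses the As-treated Population (SAP 3.4). Protocol 4.8.3.1 describes only per-arm estimates for ORR; the between-arm test appears only in the SAP.

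**The concern.** Fisher's test conditions on the total number of responders. The interval does not; it maximises over the unknown common rate. Because Fisher is the more conservative of the two at these sizes, a report could show a 95% interval for the ORR difference that excludes zero next to a p-value above the stated threshold, for one of the two co-primary endpoints. With no rule for that case, the choice of which result to emphasise would be made after the data are seen. The second cost is power: the SAP already accepts the unconditional framework for the interval, yet uses a more conservative method for the test in arms that are small.

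**Working it through.** **The plan's own figure.** The only test-power statement is in SAP 2.4.2: 85% for A vs C, 35% vs 10%, 45 vs 22, 1-sided alpha 0.10. With a pooled-variance normal approximation:

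- Pooled rate = (45×0.35 + 22×0.10)/67 = 0.268.
- SE under no difference = √(0.268×0.732×(1/45 + 1/22)) = 0.115.
- SE under the alternative = √(0.35×0.65/45 + 0.10×0.90/22) = 0.0956.
- Power = Φ((0.25 − 1.2816×0.115)/0.0956) = 85.8%.

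The 85% is reproduced. It describes neither Fisher's test nor the 2-sided 0.05 level, so it is not the benchmark for what follows.

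**Method.** All 2×2 tables were enumerated for each pair of arm sizes.

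- Fisher: two-sided p-value, rejecting if p ≤ 0.05.
- Score statistic at zero difference: z = (p1 − p2)/√(p(1 − p)(1/n1 + 1/n2)), where p is the pooled rate.
- Exact unconditional p-value: the maximum, over the common rate π, of the total probability of tables with |z| at least as large as observed. The interval excludes zero when this is ≤ 0.05 (two-sided inversion), or when the smaller one-sided version is ≤ 0.025 (two one-sided tests). Both were run because the SAP does not say which applies.

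**Sizes.** 45/45 and 45/22 are the evaluable counts in SAP 2.4.2. 50/50 is the As-treated plan (125×2/5 = 50). 26/26 and 26/13 are an assumption: Protocol 3.1.1 gives 89 enrolled in Arms A to D, the SAP plans 25 in D, and 64 split 2:2:1 is 25.6, 25.6 and 12.8. The actual arm sizes are redacted.

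**One table in full.** 13/45 is an Arm A/B count in SAP Table 2.4.2-1; 5/45 is an illustrative comparator. Difference 8/45 = 0.178; pooled rate 18/90 = 0.20; SE = √(0.16×2/45) = 0.0843; z = 2.11. The exact unconditional p is 0.045 and Fisher's p is 0.063.

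| Table | Fisher p | 95% interval, two-sided inversion | 95% interval, two one-sided |
|---|---|---|---|
| 13/45 vs 5/45 | 0.063 | 0.010 to 0.344 | 0.006 to 0.344 |
| 18/45 vs 9/45 | 0.065 | 0.008 to 0.382 | 0.006 to 0.382 |
| 20/45 vs 4/22 | 0.056 | 0.014 to 0.462 | 0.006 to 0.464 |
| 17/45 vs 3/22 | 0.051 | 0.004 to 0.426 | −0.008 to 0.432 |
| 8/26 vs 2/26 | 0.075 | 0.012 to 0.450 | 0.012 to 0.458 |

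**How often.** At 45/45, 72 of 2116 tables disagree under either inversion. At 45/22, 20 of 1058 disagree (6 with two one-sided tests). In every case the interval excludes zero and Fisher does not reject; no table went the other way.

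**Maximum size.** At 45/45: Fisher 3.2%, score test 4.9%. At 45/22: Fisher 3.7%, score test 4.9% (two-sided inversion). All stay below 5%.

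**Power at 2-sided 0.05.** Gains are from unrounded values.

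| Contrast and sizes | Rates | Fisher | Score test | Gain, points |
|---|---|---|---|---|
| A vs B, 45/45 | 35% vs 10% | 76.1% | 82.8% | 6.6 |
| A vs B, 50/50 | 35% vs 10% | 82.0% | 86.1% | about 4 |
| A vs B, 45/45 | 20% vs 5% | 48.0% | 59.4% | 11.4 |
| A vs B, 26/26 (assumed) | 35% vs 10% | 46.9% | 56.8% | about 10 |
| A vs C, 45/22 | 35% vs 10% | 56.8% | 57.3% or 59.8% | 0.6 or 3.0 |
| A vs C, 26/13 (assumed) | 35% vs 10% | 31.1% | 31.1% or 34.1% | 0 or 3.0 |

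For A vs C the first figure is for two one-sided tests and the second for two-sided inversion. Since every table that Fisher rejects is also rejected by the score test, the gain is also the probability of a contradictory report: 6.6% of trials at 45/45 with 35% vs 10%.

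**The case against.** Fisher's test is a legitimate prespecified choice: it is valid, and it also controls error conditionally on the observed margins, which the unconditional test does not. So a reader might infer that Fisher is wrong here or has no benefit, but the documents do not support that.

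The practical weight is limited. SAP 2.4.2 bases sample size primarily on precision, the p-values are unadjusted, and no decision rule in the visible text depends on this test. Arms A to C are closed, and the test does not apply to single-arm Arm E. This stands, and it makes the point an inexpensive improvement, not a threat to the trial.

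A reader might also infer a loss of about 10 points for every contrast. At 35% vs 10% that size appears only at the assumed 26/26; at the As-treated 50/50 the loss is about 4 points, and for A vs C it is 3 points or less. Nor is Fisher the main reason that A vs C power falls from 85%. Moving from 1-sided 0.10 to 2-sided 0.05 takes the same normal formula from 85.8% to 60.0%; Fisher then gives 56.8%.

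The last objection is timing. The study is open-label, interim analyses of Arms A and B preceded Amendment 6, and SAP 3.0 is dated May 2019. Moving to a test that rejects more tables could look data-driven. That stands as a cost and governs how the change must be made.

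**Conclusion.** The mismatch is real and should be resolved. The planned test and interval can contradict each other, always with the interval excluding zero and Fisher not rejecting in the sizes enumerated. For A vs B, matching the test to the interval gains about 4 to 7 points at 35% vs 10% at planned sizes, and 11.4 points at 20% vs 5% with 45/45, with exact size still below 5%. For A vs C at 35% vs 10%, the gain is 0 to 3 points.

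The results assume that the interval is the Farrington-Manning score interval named in the SAP. The A vs C range reflects the unstated inversion; for A vs B at 45/45 the inversion makes no difference. The figures at 26/26 and 26/13 also assume that Arm D enrolled exactly 25 and that the remainder split 2:2:1.

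**What to change.** In SAP 3.4.1, take the ORR p-value from the exact unconditional score test, state whether the interval inverts one two-sided test or two one-sided tests, and invert the p-value in the same way. Keep Fisher's p-value as a sensitivity result.

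Do not substitute Boschloo's test. It is unconditional but orders tables by Fisher's p-value, so it can still contradict the score interval. At 45/45 it disagrees on 8 tables (8/45 vs 2/45: Boschloo p = 0.062, score p = 0.047). At an assumed 26/13 with 35% vs 10% it disagrees in 5.6% or 8.6% of trials, depending on the inversion, against 3.0% or 0% for Fisher.

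If the sponsor prefers to keep Fisher as the planned test, the minimum is a sentence saying that the interval is primary and the p-value descriptive.

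The cost is a sentence or two and a change of test option, with no new data. The change must be entered in the SAP amendment log with its date, its reason and a statement of what A to C response data had been seen by then. The claim of exact type I error control holds only if the choice was not guided by those data.

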4.2.3 Follow-up Period

[Table 4.2.3-1](#) shows all procedures to be conducted during the end of treatment visit and follow-up period. For subjects who complete all 12 months of treatment, the last dosing visit within the 12-month period is considered to be the end of treatment visit. Subjects who discontinue before 12 months will complete the end of treatment visit at the time the decision is made to discontinue treatment.

All subjects are to complete the end of treatment visit, all follow-up visits and be contacted for survival status in accordance with the Schedule of Study Procedures. However, if a subject discontinues from treatment and moves onto alternative anticancer treatment, the follow-up visits will no longer be required; however, survival follow-up assessments would be required as indicated in the Schedule of Study Procedures unless the subject withdraws consent for further survival follow-up. Survival follow-up will continue until the end of study as defined in Section [6.3](#).

After 90 days, only subjects with investigational product-related SAEs will continue to be followed for safety.

Table 4.2.3-1 Schedule of Follow-up Procedures (as of Amendment 6)

Study Period	Follow-up Period					
	EOT ^a	Day 30 post-EOT ± 3 Days	Day 60 post-EOT ± 3 Days	Day 90 post-EOT ± 7 Days	Q3M After Day 90 post-EOT up to Month 12 post-EOT ± 7 Days	Q6M After Month 12 post-EOT ± 14 Days
██████████	█			█		
Disease assessments						
Disease assessment by RECIST v1.1 (CT or MRI) ^b	X			X	X	X
Fresh tumor biopsy	X ^c					
Subsequent anticancer therapy		X	X	X	X	X
Survival status		X	X	X	X	X
Study procedures and examinations						
Physical examination	X	X	X	X		
ECOG performance status				X	X	X
Vital signs	X	X	X	X		
12-lead ECG ^d				X		
Assessment of AEs/SAEs	X	X	X	X		
Concomitant medications	X	X	X	X		
Laboratory tests						
Serum chemistry	X	X	X	X		
Hematology	X	X	X	X		
Thyroid function tests (TSH, free T3, free T4)	X	X	X	X		
Urinalysis	X	X	X	X		
Urine or serum pregnancy test	X					

Table 4.2.3-1 Schedule of Follow-up Procedures (as of Amendment 6)

Study Period	Follow-up Period					
	EOT ^a	Day 30 post-EOT ± 3 Days	Day 60 post-EOT ± 3 Days	Day 90 post-EOT ± 7 Days	Q3M After Day 90 post-EOT up to Month 12 post-EOT ± 7 Days	Q6M After Month 12 post-EOT ± 14 Days
[REDACTED]						
[REDACTED]					[REDACTED]	
[REDACTED]					[REDACTED]	
[REDACTED]		[REDACTED]			[REDACTED]	
[REDACTED]						
[REDACTED]					[REDACTED]	
[REDACTED]					[REDACTED]	

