- DSD is defined as the time from the date of randomization for Phase 2 Arm A, B, and C subjects or the date of first dose of study treatment for Phase 1b and Phase 2 Arm D and Arm E subjects until the first date of documented PD (per RECIST v1.1), or death due to any cause, whichever occurs first. DSD will be analyzed for subjects with SD as their BOR per RECIST v1.1. The median DSD with 90% and 95% CI will be estimated based on the Kaplan-Meier curves. For subjects who are alive and progression-free at the time of data cut-off, DSD will be censored at the PFS censoring time.
- Best percentage change from baseline of the SLD of target lesions per RECIST v1.1 will be derived as the biggest decrease or the smallest increase from baseline on the SLD among all post-baseline disease assessment including unscheduled assessments. Best percentage change from baseline in the SLD of target lesions by subject will be presented in a 'Waterfall' plot, to show each subject's best percentage as a separate bar, with the bars ordered from the largest increase to the largest decrease. Additionally, the percent change from baseline in the SLD of target lesion at each post-baseline disease assessment will be summarized by treatment group with descriptive statistics.
- PFS is defined as in section 3.4.1.2. PFS-9 is the 9-month PFS rate, which is the proportion of subjects who are progression free and alive at 9 months. Similar to PFS-6, Kaplan-Meier curves will be generated for PFS and used to estimate median PFS and the PFS-9 rate along with their 2-sided 90% and 95% CIs.
- Overall survival is defined as the time from date of randomization for Phase 2 Arm A, B, and C subjects or the date of first dose of study treatment for Phase 2 Arm D and Arm E

subjects until death due to any cause. If there is no death reported for a subject by the data cut-off date, OS will be censored at last known alive date. If the last known alive date is after the data cutoff date, OS will be censored at the date of data cutoff for that subject. Kaplan-Meier curves will be generated for OS and used to estimate the median OS and the 1-year survival rate along with their 2-sided 90% and 95% CIs.

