6 APPENDIX

Table A. Statistical Analysis Plan Amendments

SAP Version	Date	Key Details of Amendment	Reason for Amendment
1.0	23MAR2016	Initial document	Initial document
2.0	18MAY2017	
 Added the sample size calculation for the new Arm E (Section 2.4.2) Analyses related to the new Arm E and some clarifications added in the efficacy analysis section (Section 3.4) 	
 To be aligned with protocol language
2.1	17APRIL2019	
 Correct exact and standard confidence intervals for ORR and PFS (Section 2.4.2) Inclusion of Arm E in the definition of OR. Correction of duration of non-treatment interval following 3 missed doses (Section 3.4.1) Inclusion of Arm E in definition of secondary efficacy endpoints. Correct method of assignment of Arm E cohort (Section 3.4.2) Correct method of assignment of Arm E cohort. Include missing multiple-item axis and single item STO22 scores for EORTC (Section 3.5.1) Editorial changes for clarity (multiple sections) 	
 Insure methods completeness for CSR development To be aligned with protocol language To be aligned with protocol language To be aligned with protocol language and EORTC scoring methodology To insure proper presentation of final CSR TFLs
3.0	15MAY2019	
 Remove multiple-item STOANX endpoint and STO22 single item endpoints from QoL summaries 	
 No clinical meaningfulness for these endpoints.

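### The SAP's single 26-week post-treatment cut-off for two or more missed scans does not match the protocol's 3-monthly then 6-monthly scans, so some late PFS events can be censored after one missed scan or none

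*SAP*

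**What the plan says.** SAP 3.4.1 back-dates PFS to the last evaluable scan, as a censoring, when progression or death comes after two or more consecutive missed or non-evaluable visits. It then converts the count into weeks: "progression or death after ≥ 2 consecutive missed disease assessment visits is defined (according to disease assessment schedules specified in the protocol"). On treatment the gap is 18 weeks, described as two visits plus a 2-week window. After EOT it is "26 weeks (three disease assessment visits plus 2 week visit window to allow for a late assessment) since the last post-baseline evaluable disease assessment", one value for all post-treatment follow-up.

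Protocol Table 4.2.3-1 (Section 4.2.3) marks follow-up disease assessments at EOT, at Day 90, then "Q3M After Day 90 post-EOT up to Month 12 post-EOT ± 7 Days", then "Q6M After Month 12 post-EOT ± 14 Days".

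SAP Table 3.4.1-1 uses counts, not weeks. It censors "Death or PD immediately after ≥ 2 consecutive missed or non-evaluable disease assessments" and treats as an event a death "after ≤1 missed or non-evaluable disease assessment following an adequate post-baseline disease assessments".

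The PFS summaries are Kaplan-Meier PFS-6 (SAP 3.4.1) and, in SAP 3.4.2, "Kaplan-Meier curves will be generated for PFS and used to estimate median PFS and the PFS-9 rate".

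**The concern.** The post-treatment figure is offered as a translation of two missed scans into weeks on the protocol schedule, but that schedule does not produce it. The label of three visits also disagrees with the count of two that it is meant to define. In the 6-monthly period 26 weeks is roughly one interval, so a progression seen at the next planned scan, or after a single missed one, can be removed as an event and back-dated. The table would keep the same subject as an event. Two programmers working from this SAP could therefore build different PFS data sets, and PFS contributes a co-primary endpoint in Arms A, B, C and E.

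**Working it through.** **Inputs.** Cut-off 26 weeks = 182 days (SAP 3.4.1). On-treatment interval 8 weeks (SAP 3.4.2: Day 113 to Day 169 = 56 days). Follow-up schedule and windows from Protocol Table 4.2.3-1: ±7 days in the 3-monthly period, ±14 days in the 6-monthly period. The documents do not fix the length of 3 months, so I take q = 84, 90 or 91.3 days. I also assume visit dates uniform within their windows.

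**Reproducing the SAP figures.**
- On treatment: 2 × 8 + 2 = 18 weeks. This agrees.
- After EOT, with the stated three visits: 3 × 8 + 2 = 26 weeks. This works only with the on-treatment interval.
- After EOT, if three is a slip for two and 3 months means 12 weeks: 2 × 12 + 2 = 26 weeks. This fits the 3-monthly period only.
- Two 6-monthly intervals plus 2 weeks would be 4q + 14 days = 350 / 374 / 379 days, or about 50 / 53 / 54 weeks.

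**Gaps that exceed the cut-off under every convention.**
- Month 12 missed, progression at Month 18: shortest gap 3q − 7 − 14 = 231 / 249 / 253 days. Always at least 182.
- One missed 6-monthly scan: shortest gap 4q − 14 − 14 = 308 / 332 / 337 days. Always at least 182.

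**Gaps that depend on the convention.** With windows of ±w at both ends and x = 182 − 2q, the chance that the gap reaches 182 days is (2w − x)² / 8w² when x ≥ 0, and 1 − (2w − |x|)² / 8w² when x < 0.

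| Progression found at | q = 84 (x = 14) | q = 90 (x = 2) | q = 91.3 (x ≈ −0.6) |
|---|---|---|---|
| On-time 6-monthly scan, none missed (w = 14) | 14²/1568 = 12.5% | 26²/1568 = 43% | 52% |
| Scan after one missed 3-monthly scan (w = 7) | 0²/392 = 0% | 12²/392 = 37% | 54% |

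An on-time 3-monthly scan is never affected: the longest gap is q + 14 = 98 / 104 / 105 days.

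**Effect on the estimates.** Censoring with nothing missed arises only in the 6-monthly period and back-dates to Month 12 post-EOT or later, so it cannot touch PFS-6 or PFS-9. Censoring after one missed scan can back-date an early discontinuer to before Month 6. Simulations comparing the 26-week rule with a count of missed scans rest on rates that are not in the documents:
- Arms of 36; median PFS 2, 4.4 or 6.6 months; 2–10% per month stopping for reasons other than progression; 5–20% of scans missed; 15% of first events deaths; 5-year cut-off. Mean PFS-6 shift −0.02 to −0.63 point, PFS-9 −0.01 to −0.32 point, median at most 0.03 month. In the harshest setting (10% per month stopping, 20% missed), 18–29% of single trials moved PFS-6 by 1 point or more.
- Median PFS 6.6 months, or median 5 with 15–25% of subjects at median 24; 10–20% stopping early; 0–10% of visits missed; 0 or 30% starting other therapy; 60-month follow-up. Over the three conventions the curve moved by −0.4 to +0.5 point at 24 months, +0.1 to +2.9 at 36 months and +0.1 to +3.8 at 48 months, with 0.2 to 3.0 of 40 subjects switching from event to censored.

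For scale, the planned 90% CI for PFS-6 in Arm E is 39% to 67% (SAP 2.4.2), a half-width of (67 − 39)/2 = 14 points.

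**The case against.** The best defence is that the governing rule in SAP 3.4.1 and Table 3.4.1-1 counts visits, and that read literally the table already gives the right answer. This stands in part: the documents do not establish that these events will in fact be censored. But the SAP says the count is defined by the week figures, so a programmer may fairly apply 182 days. The text and the table have to be reconciled.

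Second, 2 × 12 + 2 = 26 may be what was meant. That would rescue the 3-monthly period with 12-week quarters, but not the 6-monthly period under any convention. The SAP change log for version 2.1 records "Correction of duration of non-treatment interval following 3 missed doses (Section 3.4.1"). A reader might take this as proof that three is deliberate, but it speaks of doses, not scans, and settles nothing.

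Third, few subjects are exposed and no named summary is a late one. This stands. Follow-up visits stop on alternative anticancer therapy, and after confirmed progression at most the EOT scan is required (Protocol 4.2.3). The primary analysis may come after 7 months, or 5 for Arm D (Protocol 4.8.1). A subject who completes treatment enters the 6-monthly period only at about Day 351 + 360 to 365 = Day 711 to 716. That is within reach: SAP 3.0 (15MAY2019) is 841 days after Amendment 6 (24Jan2017), by which time 89 Phase 2 subjects were enrolled, and follow-up may run to 5 years. But the data cut-off is not given, and final analyses cover only selected endpoints.

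**Conclusion.** The post-treatment definition is wrong as written: it cites a schedule that it does not follow, and it can contradict Table 3.4.1-1 for the same subject. The firm part is arithmetic. One missed scan involving a 6-monthly interval always puts a progression past 26 weeks. The shares for on-time 6-monthly scans and for one missed 3-monthly scan depend on the month convention and on uniform visit dates.

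The severity is minor. A reader might infer that the co-primary PFS-6 is materially biased. The documents do not support that: the mean shift stays under about 1 point in every assumed scenario, and PFS-9 and the median move less. Nor can a tight bound be claimed, because the stopping and missed-scan rates are assumptions and single trials can move more than the mean. The main effect is an upward bias in the late part of the planned PFS curve, and it matters only if long follow-up is shown.

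**What to change.** Delete the 26-week, three-visit definition for the post-treatment period. Derive two or more consecutive missed scans by counting protocol-scheduled scans, including EOT and Day 90, whose window closed without an evaluable assessment. State the month convention, set an analysis window for the EOT scan (Table 4.2.3-1 shows none), and make Table 3.4.1-1 refer to this definition.

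Separate week cut-offs for each period are tempting but not clean, because they overlook the EOT scan. Take a completer last scanned at Day 337 who misses EOT (Day 351) and Day 90 and progresses at Month 6 post-EOT. Two scans are missed and the nominal gap is 14 + 2q = 194 or 197 days with q = 90 or 91.3. With windows of ±3 and ±7 days the present rule always censors this subject, since the shortest gap is 184 or 187 days. A cut-off of two 3-monthly intervals plus 2 weeks is also 2q + 14 days, so it would censor only about half.

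The cost is one SAP wording and derivation change. Late PFS may look slightly shorter.
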